6.3 Additional Endpoints

- Total procedure time, ablation time, RF application time, balloon dwell time, time to effect (PVI)
- Number and time of RF applications per PV location
- Fluoroscopy time and dose

6.4 Health Economic Data

- Index procedural workflow costs
- Hospital costs
- Quality of Life: Atrial Fibrillation Effect on QualiTY-of-life (AFEQT) questionnaire

7 LEVEL OF SIGNIFICANCE

Each of the primary safety and effectiveness hypothesis tests will be performed at a one-sided 5.0% significance level. The safety of this device was initially assessed in a feasibility study, and a safety event rate of 2.6% (1 in 39 patients) was observed. Given the available data on subjects from the feasibility study it was concluded that the proposed study could provide sufficient evidence for safety of the device using a type-I error of 5%, rather than requiring the conventional two-sided 5%. Since study success is defined as meeting both endpoints and the type-I error for each test is controlled at 5.0%, the type-I error for claiming study success is controlled at 5.0%. In addition, we have demonstrated that the overall type-I error for study success is controlled at 5.0% for all hypothetical scenarios simulated including the ones where one or both safety and effectiveness rates are on the decision boundary.

8 ANALYSIS SETS

8.1 Main Study

For the analysis of study endpoints, the analysis populations defined in the following will be used:

- **Modified Intent-To-Treat (mITT) Population:** The mITT population will consist of enrolled subjects who meet eligibility criteria and have undergone insertion of the study catheters.
- **Safety Population (SP):** The SP will consist of all enrolled subjects who have undergone insertion of the study catheters.
- **Per Protocol (PP) Population:** The PP population is a subset of the mITT population and will include subjects who comply with the following criteria:
 - are enrolled and meet all eligibility criteria
 - have undergone RF ablation with study catheters
 - are treated for the study-related arrhythmia

Neurological Assessment Evaluable (NAE) Population: The NAE Population will include at least 40 subjects who are subset of the Per Protocol Population, consent and are eligible for the required neurological assessments, and have post-ablation MRI. Assessment of incidence of new lesions requires availability of pre-and post MRI. The subjects without pre-MRI but no lesion on post-MRI will be included in the NAE population. Assessment of incidence of new deficits requires availability of pre-and post-neurological evaluation. Enrollment in the NAE population may be terminated prior to achieving the target number of subjects if study enrollment ends early after a planned interim look.

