**Cerebral ischemic lesions:** The incidence of transient ischemic attack (TIA) is <3% following CB-2 ablation, however, in most studies imaging for silent ischemic brain lesions was not performed. In one study in which post procedural imaging was obtained, 13.6% of LB-treated patients were observed to have new embolic brain lesions, and another 2.3% had diplopia secondary to an ischemic lesion. There were similar findings of diplopia due to a suspected ischemic event (1.4%) in another LB study. The incidence of asymptomatic cerebral lesions seen on MRI 1-2 days post-procedure in a randomized controlled study was 24% for LB, which was not significantly different from RF catheter ablation or first-generation CB. According to HRS guidelines, 2017, Asymptomatic cerebral emboli (ACE) incidence is varying from 2%-15% as a complication to AF ablation. It is defined as an occlusion of a blood vessel in the brain due to an embolus that does not result in any acute clinical symptoms and is therefore 'silent'. Emboli can result from a thrombus, gas, air, tissue or fat. Source of micro-emboli include thrombi, which can develop on sheaths, materials, air introduction through sheath or during catheter exchange.

**Coronary artery occlusion:** RF current may cause occlusion of a coronary artery, either by direct thermal damage, spasm, or thrombosis. Research suggests that the risk of coronary occlusion is less than 0.5%. Because coronary arterial occlusion could produce myocardial infarction, angina or death, the physician will attempt to restore coronary blood flow through pharmacological, catheter and/or surgical intervention as medically indicated.

**Heart block:** The application of RF current close to the AV node or HIS bundle could damage or destroy the normal AV conduction system, producing complete heart block and requiring implantation of a permanent pacemaker.

**Cardiac perforation:** Cardiac perforation may result from catheter manipulation or application of RF current (risk is <1%). This may result in cardiac tamponade and may require percutaneous pericardial drainage or surgical repair. However, the risk of perforation related to a deep steam pop is reduced if RF energy is not delivered perpendicular to the wall at power above 35 or 40 watts. If the lesion is deeper, the risk of steam pop is higher above 35-40 watts.

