## 4.4 Subject Enrollment Disposition

- **Enrolled Subjects:** Patients who sign the informed consent form.
- **Evaluable Subjects:** All enrolled subjects who have the study catheter inserted.
- **Excluded Subjects:** Subjects who are enrolled but never undergo insertion of the study catheter. Excluded subjects will only be followed between ICF signature and exclusion for event reporting.
- **Roll-In Subjects:** Enrolled Subjects who have the study catheter inserted and RF delivered during the roll-In phase of the ablating investigator. These subjects will not be included in the main study analyses and will be analyzed separately.
- **Discontinued Subjects:** Enrolled subjects who have the study catheter inserted but do not undergo ablation (i.e., no RF energy is delivered with the study catheter). Discontinued subjects will remain in follow-up for 30 days.
- **Lost to Follow-up Subjects:** Evaluable subjects of which contact is lost after most recent visit (despite 3 documented attempts to contact the subject).
- **Withdrawn / Early Termination Subjects:** Subjects who withdraw consent for study participation or are withdrawn by the investigator, are terminated from the study prior to completion of all follow-up visits.
- **Completed Subjects:** Enrolled subjects who have not been excluded, discontinued, withdrawn, terminated early, or lost-to-follow-up from the study prior to the final study visit.

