## 8 Study Schedule

### 8.1 Screening and Informed Consent

Subjects presenting to the institution with symptomatic PAF and considered for an RF ablation procedure should be screened by the investigator or designated member of the research team for study eligibility per the protocol inclusion and exclusion criteria. Sites will be instructed to screen all subjects who require a documented RF ablation procedure for symptomatic PAF without regard to sex or race.

The study investigator or designated member of the research team will obtain written informed consent from the subject. The patient informed consent procedure must be done within 60 days before the actual study procedure takes place. The background of the proposed study and the potential benefits and risks of the study should be explained to the subject. The subject or legal representative must sign the consent form prior to any study-specific exams or tests are provided to them that fall outside of the standard of care. The consent form used must have prior approval from the regulatory authorities and study site's Ethics Committee. Failure to obtain informed consent renders the subject ineligible for participation in the study.

The investigator and/or designee must also clearly document the process of obtaining informed consent in the subject's source documents. The voluntary process of informed consent confirms the subject's willingness to participate in the study. It's the investigator's responsibility to ensure that the informed consent process is performed in accordance with ICH-GCP and with applicable local and federal regulations. If new information becomes available that can significantly affect a subject's future health and/or medical care, this information shall be provided to the subject(s) affected in written form. If relevant, all affected subjects shall be asked to confirm their continuing informed consent in writing by dating and signing an amended ICF.

Each subject screened for enrollment in the clinical investigation who signs the patient informed consent form will be enrolled into the study. Each eligible subject who signs the informed consent on the additional neurological assessments and has post-MRI completed will be included in the NAE subgroup. No subject should undergo any clinical investigation specific tests or examinations that fall outside the standard of care without first signing the patient informed consent form for this clinical investigation.

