## 14 Statistical Methodology

### 14.1 Analysis Population

#### 14.1.1 Main-Study

- **Modified Intent-To-Treat (mITT) Population:** The Modified Intent-To-Treat (mITT) population consists of enrolled subjects who meet eligibility criteria and have the study catheter inserted.
- **Safety Population (SP):** The Safety Population will consist of all enrolled subjects who have undergone insertion of the study catheter.
- **Per Protocol (PP) Population:** The PP population is a subset of the mITT population and will include subjects who comply with the following criteria:

- Are enrolled and meet all eligibility criteria
  - Have undergone RF ablation with the study catheter
  - Have been treated for the study-related arrhythmia
- **Neurological Assessment Evaluable (NAE) Population:** The NAE Population will include at least 40 subjects who are subset of the Per Protocol Population, consent and are eligible for the required neurological assessments, and have post-ablation MRI. Assessment of incidence of new lesions requires availability of pre-and post MRI. Assessment of incidence of new deficits requires availability of pre-and post-neurological evaluation. Enrollment in the NAE population may be terminated prior to achieving the target number of subjects if study enrollment ends early after a planned interim look.

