### 14.8.6 Analyses of Secondary and Additional Endpoints

Percentage (%) of subjects with freedom from documented symptomatic atrial fibrillation (AF), atrial tachycardia (AT), or atypical (left side) atrial flutter (AFL) episodes will be estimated in the mITT population at 180 and 365 days with the corresponding one-sided 95% exact binomial lower bound.

Descriptive statistics will be presented for the remaining secondary endpoints in the Safety and mITT Populations overall and by roll-in cases. The neurological assessment related endpoints will be analyzed in the NAE population. No formal statistical hypotheses and

inferential statistics will be formulated and performed for the remaining effectiveness and safety endpoints. Details of analyses methods for secondary and additional endpoints will be provided in SAP.

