11.5.3 NAE Endpoints

The occurrences of asymptomatic and symptomatic cerebral emboli will be summarized by timepoints of pre- and post-ablation procedure. Frequency, anatomic location, and size (diameter and volume) of cerebral emboli at baseline, post-ablation and during follow-up will also be

Biosense Webster, Inc

summarized. Neurologic deficits observed post ablation and during follow up period will be summarized.

The National Institutes of Health Stroke Scale (NIHSS) scores and Montreal Cognitive Assessment (MoCA) scores at baseline, post ablation and during follow-up will be summarized with descriptive statistics.

These analyses will be performed in the NAE population.

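### The neurological sub-study's clinical endpoints (new deficits, NIHSS, MoCA) are confined to per-protocol subjects with a post-ablation MRI, although assessing them needs neither RF delivery nor a scan

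*SAP*

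**What the plan says.** SAP 8.1 builds the NAE population from three layers: per-protocol status, consent and eligibility for the neurological work-up, and a completed scan. Members must be a "subset of the Per Protocol Population, consent and are eligible for the required neurological assessments, and have post-ablation MRI". Per-protocol status in turn requires that subjects "have undergone RF ablation with study catheters". Protocol 14.1.1 has the same definition. Protocol 8.1 is looser: an eligible subject who consents to the assessments and "has post-MRI completed will be included in the NAE subgroup", with no mention of RF or per-protocol status.

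SAP 11.5.3 lists cerebral emboli, neurologic deficits, NIHSS and MoCA together and closes with "These analyses will be performed in the NAE population". Protocol 14.8.6 agrees: "The neurological assessment related endpoints will be analyzed in the NAE population". Neither document plans a second analysis of these endpoints in a wider set.

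For the deficit endpoint, both documents state the data actually needed: "Assessment of incidence of new deficits requires availability of pre-and post-neurological evaluation". That sentence does not mention imaging, but it is applied inside a population already restricted by imaging.

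**The concern.** These are secondary safety endpoints (Protocol 3.2.2, SAP 6.2.1). The other secondary safety endpoints are analysed in the Safety and mITT populations (SAP 11.5.1), where entry depends on catheter insertion (plus eligibility for mITT). The NAE clinical endpoints add two conditions that are settled only after the catheter is in: whether RF was delivered and whether a scan was completed. Either can depend on what happened to the patient. A procedure stopped for a complication yields no RF; a subject who is unwell may miss the scan.

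Exposure to embolic risk does not begin with RF. Protocol 1.4.1 says: "Source of micro-emboli include thrombi, which can develop on sheaths, materials, air introduction through sheath or during catheter exchange". Conditioning a neurological safety summary on RF delivery can therefore remove subjects who were exposed.

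At stake is how well the sub-study describes neurological status after use of the device. The plan describes it among subjects who were ablated and scanned, and sets aside completed examinations from anyone else.

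**Working it through.** The plan gives no precision or power figure for the NAE subgroup, only its target of 40 (Protocol 3.1.3), so there is nothing to reproduce. The check is a reading of definitions, followed by a small illustration.

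**1. Data needed against conditions imposed**

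| Endpoint | Data needed | RF required by the plan | MRI required by the plan |
|---|---|---|---|
| New cerebral lesions | pre- and post-procedure MRI | yes | yes (unavoidable) |
| New or worsening deficits | pre- and post-procedure neurological evaluation | yes | yes |
| NIHSS | scale at baseline, within 48 hours, later if indicated | yes | yes |
| MoCA | scale at baseline, 1 month, later if indicated | yes | yes |
| Individual PAEs, SAEs, non-serious AEs | event report | no | no |

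The timings are from Protocol 8.2.1, 8.2.4 and 8.3; the populations are from SAP 8.1, 11.5.1 and 11.5.3.

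**2. Two subjects traced through the definitions**

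- Subject A consents to the sub-study, receives RF, and has the examination and NIHSS within 48 hours, but never has a post-ablation MRI. A is in the Safety, mITT and PP populations but not in NAE, so the completed examination and scores are not summarised.
- Subject B consents and has the catheter inserted, but no RF is delivered. Protocol 4.4 calls B discontinued and says: "Discontinued subjects will remain in follow-up for 30 days". The 48-hour examination falls well inside that period, and the 1-month visit (day 23 to 37) partly does. B is outside PP and hence outside NAE even if scanned, although Protocol 8.1 taken alone would put a scanned B in the subgroup.

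**3. Where A and B are still counted**

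Stroke/CVA, TIA and thromboembolism are Primary Adverse Events. They are analysed in mITT (SAP 11.4.2), repeated in the Safety Population (SAP 11.4.5), and summarised by type, with SAEs and non-serious AEs, in both (SAP 11.5.1). Protocol 9.1.1 also makes a new or worsened physical finding an adverse event. What disappears is (a) A's and B's contribution to the NAE deficit incidence and score summaries and (b) any NIHSS or MoCA change that nobody reported as an adverse event.

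**4. Illustrative size**

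The number of subjects affected is an assumption. NAE members are by definition already scanned, so an omitted case lies outside the 40 and is added to both numerator and denominator. The exact one-sided 95% upper bound is the p that solves P(X ≤ x | n, p) = 0.05; for x = 0 it is 1 − 0.05^(1/n).

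- None restored: 0/40 = 0%; bound 1 − 0.05^(1/40) = 7.2%.
- One restored: 1/41 = 2.4%; bound 11.1%.
- Two restored: 2/42 = 4.8%; bound 14.2%.
- Three restored: 3/43 = 7.0%; bound 17.1%.

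**5. Likely frequency**

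Protocol 1.2.3 reports 39 treated feasibility subjects and 39 with a post-ablation MRI, so none was lost for want of a scan. With 0 of 39, an unscanned rate up to 1 − 0.05^(1/39) = 7.4% is not ruled out, which in 40 subjects is 0.074 × 40 ≈ 3. Only a fraction of those would have a deficit. The documents give no rate for catheter insertion without RF.

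**The case against.** A reader might infer that all neurological safety results are restricted in this way and that a patient with a new deficit is dropped from the trial. The documents do not support that: as traced above, clinically reported events reach the mITT and Safety tables with no RF or MRI condition.

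Several further points count against a strong version.

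- The NAE definition sets no time limit for the scan, and note 10 to Protocol Table 8.7 A allows a missed mandated test to be made up at an unscheduled visit. A subject too unwell to be scanned within 48 hours may still qualify.
- Symptoms tend to prompt imaging. Notes 9 and 10 call for or allow it, the TIA definition refers to neuroimaging, and imaging is one way to confirm a stroke. The MRI condition need not select against symptomatic subjects. If it mainly removes deficit-free subjects it raises the rate slightly, for example 1/40 = 2.5% against 1/41 = 2.4%.
- The feasibility subject with an air embolism at sheath insertion was one of the nine with new lesions, so that subject was scanned and counted.
- The sub-study is chiefly about cerebral emboli seen on MRI, and an MRI-evaluable set is a natural choice for that purpose.
- The endpoints are descriptive (SAP 11.5), so the bounds above are a gauge of precision and not planned outputs.

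All of this stands and limits the size of the problem. None of it gives a reason to require RF or a scan before summarising a neurological examination, and a later MRI cannot help a subject who is outside PP for lack of RF.

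**Conclusion.** The point holds for the clinical endpoints of the NAE sub-study: new or worsening deficits, NIHSS and MoCA. Their analysis set carries two conditions that these endpoints do not need, that are settled after catheter insertion, and that can depend on harm. Limiting the MRI lesion endpoints to scanned subjects is proper.

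Severity is minor to moderate. The primary safety test is unaffected and reported clinical events are counted elsewhere. The frequency is unknown and probably low. With about 40 subjects, however, one omitted case is the difference between no deficits and 2.4%, and the NAE deficit table would then disagree with the adverse-event tables in the same report.

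The illustration assumes exactly 40 scanned subjects, no deficits among them, and one to three omitted subjects each with a deficit. A reader might also infer that the deficit rate is understated by some stated percentage; the documents offer no basis for such a figure, and the direction of any effect from the MRI condition alone is not certain.

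**What to change.** In SAP 8.1 and 11.5.3, with Protocol 8.1, 14.1.1 and 14.8.6 brought into line:

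- Analyse new or worsening deficits, NIHSS and MoCA in all non-roll-in subjects who consented to the neurological assessments, had the study catheter inserted, and have a baseline and at least one post-procedure neurological evaluation, whether or not RF was delivered or an MRI done.
- Keep the MRI requirement for the lesion endpoints only.
- List consented subjects without a post-ablation MRI, with the reason and their neurological status.
- Keep the present NAE set as a supportive summary.

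The cost is SAP wording, one additional table and a listing, using assessments already planned. Denominators for the clinical and MRI endpoints may differ by a few subjects, which a footnote can explain. The change does not reach a subject whose procedure is abandoned at the sheath stage, before the study catheter is inserted; under Protocol 4.4 such a subject is excluded and followed only until exclusion.

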8.2 Roll-in

- **Roll-In Population:** The Roll-In population will include all subjects who are enrolled in the roll-in phase and have the study catheter inserted and RF delivered. All endpoints will be analyzed for the roll-in population separately.

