#### 3.1.1 Roll-In Subjects

One key purpose of this study will be to demonstrate the acute effectiveness of the multi-electrode RF balloon catheter in the absence of confounding evidence that reflects early stages of a medical device learning curve. In addition to a requirement for multi-electrode RF balloon catheter training prior to each ablating physician's participation in this study, additional experience of the multi-electrode RF balloon use, in the context of this clinical investigational plan, would serve to generate a clearer perspective of the multi-electrode RF

catheter acute effectiveness in treating PAF subjects. Therefore, to minimize the learning curve effect of using the multi-electrode RF balloon catheter, roll-in subjects will be prospectively assigned to each ablating physician per the training plan specifically designed for this study.

- 1 roll-in subject will be included for ablating physicians that participated in the RADIANCE Study
- 2 roll-in subjects will be included by ablating physicians that didn't participate in the RADIANCE study and have extensive balloon experience (>15 cases/year)
- 3 roll-in subjects will be included by ablating physicians that didn't participate in the RADIANCE study and don't have extensive balloon experience (<15 cases/year), to minimize the learning curve effect of

A subject who is excluded or discontinued will not count toward the roll-in subjects. All roll-in subjects will be followed for 12 months post-procedure. The roll-in subjects will be excluded from the main study analyses and will be analyzed separately.

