#### 14.1.2 Roll-In

- **Roll-In Population:** The Roll-In population will include all subjects from the roll-in phase of the ablating physician that have the study catheter inserted. All endpoints will be analyzed for the roll-in population separately.

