11.4.5 Sensitivity Analyses

To investigate the robustness of the primary safety endpoint results, the following sensitivity analyses will be performed.

1) Tipping Point Analysis in mITT Population

In this study, the tipping point is defined as the number of subjects with primary AEs for the binary safety endpoint in the study population at which the study conclusion is changed. The tipping-point analysis will replace the missing values with primary AE occurrence one at a time and the corresponding exact one-sided 95% upper confidence bound will be produced³. The confidence bound is calculated to test the PAE rate against the performance goal of 15%. If the exact one-sided 95% upper confidence bound calculated based on the imputed number of PAEs leads to a change in the study conclusion, then the imputed number of PAEs will be considered the tipping point.

The tipping-point analysis for binary safety endpoints will analyze all possible cases that may occur in the missing data cohort. The results will be presented in a summary table to illustrate how the exact one-sided 95% upper confidence bound and the conclusion on meeting the performance goal change.

2) Primary Safety Analysis in Safety Population

The primary safety analysis will be repeated in the Safety Population to include all enrolled subjects who had study catheter inserted in the evaluation of safety. The analysis is based upon data available and the early onset PAEs will be carried forward. The exact binomial proportion will be presented together with the one-sided 95% upper bound of the confidence interval.

To investigate the robustness of the primary effectiveness endpoint results, the primary effectiveness analysis will also be performed in the Safety Population for all enrolled subjects who had study catheter inserted and RF delivered with study catheters. The analysis is based upon data available. The exact binomial proportion will be presented together with the one-sided 95% lower bound of the confidence interval.

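### A roll-in-phase subject with the catheter inserted but no RF delivered is left out of the SAP's roll-in safety rate and has no clearly assigned safety set

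*SAP*

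**What the plan says.** Two definitions of the roll-in group are in force.

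- **Insertion only.** Protocol 14.1.2, the protocol's analysis-population section: "The Roll-In population will include all subjects from the roll-in phase of the ablating physician that have the study catheter inserted".
- **Insertion and RF.** SAP 8.2 adds the condition "have the study catheter inserted and RF delivered". Protocol 4.4 has the same condition for a Roll-In Subject: "Enrolled Subjects who have the study catheter inserted and RF delivered during the roll-In phase of the ablating investigator".

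Protocol 4.4 classes as Discontinued the "Enrolled subjects who have the study catheter inserted but do not undergo ablation" and follows them for 30 days. Protocol 3.1.1 adds: "A subject who is excluded or discontinued will not count toward the roll-in subjects".

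For the other safety sets, SAP 8.1, under the heading Main Study, states: "The SP will consist of all enrolled subjects who have undergone insertion of the study catheters". SAP 11.4.5 describes a sensitivity analysis of primary safety "repeated in the Safety Population to include all enrolled subjects who had study catheter inserted". Protocol 3.1.1, 3.2.2 and 4.4 keep roll-in subjects out of the main analyses and have them analysed separately. SAP 11.4.2 and 11.5.1 call for primary and secondary safety results in the roll-in subjects.

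**The concern.** A safety set defined by RF delivery depends on the procedure having got that far. Cardiac tamponade or perforation and major vascular access complication or bleeding are components of the primary adverse event (PAE) composite, and neither needs RF to occur. Such an event may be the reason the operator stopped before delivering RF. The condition can therefore select on the outcome, and it does so in the operators' first cases, which the roll-in phase exists to describe separately.

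Two things are at stake. The learning-phase PAE rate may be understated. And because the documents do not place this subject, the same case could be missing from every safety rate or be counted in the main study that the roll-in phase is meant to protect.

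**Working it through.** The plan states no figure on this point, so there is none to reproduce. The check is a comparison of definitions, followed by a calculation for scale.

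**Step 1. Place one subject: roll-in phase, catheter inserted, no RF, PAE on insertion.**

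| Set | Source | Is the subject in? |
|---|---|---|
| Roll-In Population | Protocol 14.1.2 | Yes |
| Roll-In Population | SAP 8.2 | No, RF required |
| Roll-In Subject | Protocol 4.4 | No, RF required |
| Count of roll-in cases | Protocol 3.1.1 | No, discontinued |
| Per Protocol | SAP 8.1 | No, RF ablation required |
| Safety Population | SAP 8.1 and 11.4.5 | Unclear |
| mITT | SAP 8.1 | Unclear; at most if eligible |

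**Step 2. Why the last two rows are unclear.**

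- *Reading A, excluded.* SAP 8.1 is headed Main Study, and the Protocol Summary describes evaluable patients as those with the catheter inserted apart from roll-ins. The subject is then in no SAP analysis set.
- *Reading B, included.* The Safety Population sentence has no roll-in exclusion and no RF condition. Under Protocol 4.4 a subject without RF is Evaluable and Discontinued, not a Roll-In Subject, so the exclusion of roll-in subjects does not clearly apply.

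**Step 3. Effect on the roll-in rate.** Inputs: the documents estimate up to 60 roll-ins (Protocol Summary; SAP 1). Assumption: 60 subjects with RF plus one further insertion-only subject with a PAE. The exact one-sided 95% upper bound for x events in n is the 0.95 quantile of Beta(x+1, n−x). For x = 0 this is 1 − 0.05^(1/n), so for n = 60 it is 1 − 0.05^(1/60) = 4.87%.

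| Other events | Subject omitted | Subject included | Shift in rate | Shift in bound |
|---|---|---|---|---|
| 0 | 0/60 = 0.00%, bound 4.87% | 1/61 = 1.64%, bound 7.54% | 1.64 points | 2.67 points |
| 3 | 3/60 = 5.00%, bound 12.42% | 4/61 = 6.56%, bound 14.38% | 1.56 points | 1.96 points |

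**Step 4. Effect on the main test under Reading B.** The most PAEs that keep the upper bound below the 15% goal are:

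| n | Largest passing count (bound) | One more event (bound) |
|---|---|---|
| 80 | 6 (14.27%) | 7 (15.81%) |
| 130 | 12 (14.53%) | 13 (15.43%) |
| 180 | 18 (14.47%) | 19 (15.10%) |
| 230 | 25 (14.85%) | 26 (15.34%) |

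One learning-phase event changes the primary safety conclusion only if the count is already at the limit.

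**Step 5. Follow-up.** Protocol 4.4 follows discontinued subjects for 30 days. Three PAE components run to 90 days (Protocol 3.2.1), and phrenic nerve paralysis is judged at the 3-month visit (Protocol 9.1.3). SAP 11.4.2 drops subjects without full follow-up unless they had a PAE. The documents do not say whether 30 days counts as full follow-up for a discontinued subject. If it does not, adding insertion-only roll-ins under the present rule would keep those with an event and drop those without, which biases the rate upward.

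**The case against.** The strongest reply is that the SAP did not depart from a consistent protocol. Protocol 4.4 has the same RF condition, 3.1.1 agrees with it, and SAP 11.2 takes its disposition categories from 4.4. This stands: the conflict is inside the protocol as well, and editing SAP 8.2 alone would not settle it.

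A reader might infer that the subject is certainly in no analysis set. The documents do not support that. It holds only if the Main Study heading overrides the literal wording of the Safety Population. Against the literal wording, it would also admit every ordinary roll-in subject, contrary to the separate analysis of roll-ins. But Protocol 4.4 gives an insertion-only subject a different label from those roll-ins, so neither reading is closed off.

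A reader might also infer that the harm would go unseen. It would not. Adverse events are recorded from consent, serious and primary events go to the sponsor within 72 hours, safety data are reviewed under Protocol 9.5, and discontinued subjects appear in the disposition table. What is at risk is the event's place in a reported safety rate.

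Finally, roll-in results carry no performance-goal decision, and the number of insertion-only roll-ins is unknown and may be zero. Both points stand and keep this minor.

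**Conclusion.** The point holds as a definitional conflict with a small but real safety consequence. SAP 8.2, Protocol 4.4 and Protocol 3.1.1 disagree with Protocol 14.1.2. If the SAP is followed, insertion-only roll-in-phase subjects leave the roll-in safety rate and have no clearly assigned safety set.

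The effect is about 1.6 points on the roll-in PAE rate and 2 to 3 points on its upper bound per omitted event. This assumes 60 RF-treated roll-ins and one such event; the documents do not give the expected number of subjects without RF. The main primary tests are unaffected if the subject is left out of the mITT. If the subject is counted there, the result could change only at the boundary counts. This is a low-severity correction, worth making because it is cheap and removes a possible selection on outcome.

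**What to change.** 1. In SAP 8.2, define the roll-in safety set as all roll-in-phase subjects with the study catheter inserted, as in Protocol 14.1.2. Apply the RF condition only to roll-in effectiveness and procedural tables.
2. In SAP 8.1, state that the Safety Population and mITT exclude every roll-in-phase subject, whether or not RF was delivered.
3. Reconcile Protocol 4.4 and 3.1.1 with this. They can still govern how many roll-in cases an operator must complete, provided they are said not to define the safety set.
4. In SAP 11.4.2, keep insertion-only roll-in subjects in the roll-in safety denominator on available data, so that the full-follow-up rule does not retain only those who had an event. Report how many there are and how long they were followed.

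The cost is a few sentences, no new data collection, and a roll-in PAE rate that may be slightly less favourable.
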